No study to date, however, compared efficacy of iron carboxymaltose to iron isomaltoside for treatment of postpartum anemia. The only head-to-head comparison between these two compounds merely examined economic aspects of each treatment, showing potential reduction of costs associated with the use of iron isomaltoside vs. iron carboxymaltose (27).

OBJECTIVE

The objective of the study is to compare efficacy of intravenous iron carboxymaltose to intravenous iron isomaltoside and oral iron sulphate for treatment of postpartum anemia.

METHODS

Single-center, randomized, open-label trial.

Inclusion criteria

Postpartum patients with a hemoglobin level between 70 g/L and 100 g/L within 48 hours after delivery.

Exclusion criteria

- Contraindications for any of the study drugs.
- Anemia due to causes other than iron deficiency.
- Signs of systemic infection.
- Renal or hepatic dysfunction.
- Depression during pregnancy or pre-existing depressive disorders.

After signed informed consent patients will be allocated randomly in a 1:1:1 fashion into one of three groups:

1. Iron carboxymaltose group. Total dose of intravenous ferric carboxymaltose (Iroprem®) needed to correct anemia and replenish iron stores will be calculated using the Ganzoni formula (28) modified to include adjustment for baseline iron status: prepregnancy weight in kilograms X (15–baseline Hb) X 2.4 + 500. Fifteen is the target Hb in g/dL, 2.4 is a unit less conversion constant and 500 is the target iron stores in mg. The maximal dose administered in a single day will not exceed 15 mg/kg (current weight) or 1000 mg (for participants with body weight > 67 kg). If total calculated dose will exceed 15 mg/kg or 1000 mg, subsequent doses will be administered weekly until the total calculated dose will be reached.
2. Iron isomaltoside group. Total dose of intravenous iron isomaltoside (Monofer®) needed to correct anemia and replenish iron stores will be calculated as described above. The maximal dose administered in a single day will not exceed 20 mg/kg (current weight) or 1500 mg (for participants with body weight > 75 kg). If total calculated dose will exceed 20 mg/kg or 1500 mg, subsequent doses will be administered weekly until the total calculated dose will be reached.

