3. Iron sulphate group. Participants will receive oral ferrous sulphate (Tardyfer®) 160 mg daily for 6 weeks with instruction to take two tablets by mouth once daily 1 hour before meal. They will receive no additional iron supplementation.

We will monitor blood pressure and record adverse events in all patients before and after administration of IV iron and ask all patients to report any untoward medical event at its onset.

Outcomes

Primary outcome

- Multidimensional Fatigue Inventory (MFI) score at 6 weeks postpartum. The MFI evaluates five dimensions of fatigue: general fatigue, physical fatigue, reduced activity, reduced motivation, and mental fatigue, and consists of 20 statements for which the participant indicates, on a five-point scale, the extent to which the particular statement applies with regard to aspects of fatigue experienced during the previous days. Higher scores indicate a higher degree of fatigue.

Secondary outcomes

- Edinburgh Postnatal Depression Scale (EPDS) score at 6 weeks postpartum. EPDA is a 10-item questionnaire which evaluates different depression symptoms, such as guilt feeling, sleep disturbance, low energy, anhedonia, and suicidal ideation. Overall assessment is done by total score, which is determined by adding together the scores for each of the 10 items. Higher scores indicate more depressive symptoms.
- Mean hemoglobin level at 6 weeks postpartum.
- Proportion of participants with hemoglobin level > 120 g/L at 6 weeks postpartum.
- Proportion of participants with ferritin level > 50 mcg/L at 6 weeks postpartum.
- Mean reticulocyte count at 6 weeks postpartum.
- Mean ferritin level at 6 weeks postpartum.
- Mean transferrin level at 6 weeks postpartum.
- Costs of treatments
- Compliance with oral ferrous sulphate treatment
- Side effects of all three study treatments in mothers (e.g. constipation, headache, infusion site burning) and infants (e.g. constipation, erythema, diarrhea, abdominal pain, upper respiratory tract infection)

Statistical analysis

The planned sample size of 100 patients per group was based on a 80% power to detect non-inferiority using a margin of 5 (half the estimated clinically relevant difference in MFI), an α of 0.01, and expected standard deviation (SD) of 10, with a 20 % dropout rate.

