All data will be analyzed according to a pre-established statistical plan. Statistical analyses will be performed with SPSS software (version 24.0; IBM Corporation, Armonk, New York). Data will be entered as numerical or categorical, as appropriate. Shapiro-Wilk test will be used to assess normality of distribution. Parametric statistics will be carried out for normally distributed variables; for non-normal distribution, we will use nonparametric statistics. Data with normal distribution will be described using minimum, maximum, and mean with standard deviation. Data with non-normal distribution will be described using minimum, maximum, median, and interquartile range (IQR). Comparisons will be carried out between the study groups using independent Student's t test or Mann-Whitney U test for continuous and with Chi-square test for categorical variables.

REFERENCES

8. Cook JD. Diagnosis and management of iron-deficiency anaemia. *Best Pract Res Clin Haematol.* 2005;18(2): 319-32

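### The trial is sized for non-inferiority on the 6-week MFI score, but the stated analysis is a difference test that uses no margin and names no pair or reference arm

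*Combined protocol and SAP*

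**What the plan says.** The primary outcome is the "Multidimensional Fatigue Inventory (MFI) score at 6 weeks postpartum", with higher scores meaning more fatigue. The sample-size sentence under Statistical analysis reads: "The planned sample size of 100 patients per group was based on a 80% power to detect non-inferiority using a margin of 5". It explains the margin as "half the estimated clinically relevant difference in MFI", which implies a relevant difference of 10 points, and adds alpha 0.01, SD 10 and 20% dropout. It does not state the sidedness, the assumed true difference or the pair of arms.

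The rest of the section gives one analysis for all continuous outcomes: "Comparisons will be carried out between the study groups using independent Student's t test or Mann-Whitney U test for continuous" variables, after "Shapiro-Wilk test will be used to assess normality of distribution". It mentions no margin, shifted null hypothesis, confidence interval or decision rule. It also says: "All data will be analyzed according to a pre-established statistical plan". The content of that plan is not in the supplied document.

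The Objective covers three arms: "The objective of the study is to compare efficacy of intravenous iron carboxymaltose to intravenous iron isomaltoside and oral iron sulphate". The Rationale ends by pointing to one gap: "No study to date, however, compared efficacy of iron carboxymaltose to iron isomaltoside for treatment of postpartum anemia".

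**The concern.** A non-inferiority trial is decided by comparing a confidence limit with the margin, or equivalently by testing against a null shifted to the margin. The section sets a margin to obtain the sample size and then does not use it. A t test or Mann-Whitney test with no stated null is ordinarily a test of no difference. Its p-value does not answer whether the test arm is less than 5 points worse.

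Two further gaps follow. Non-inferiority is directional, so the text must say which arm is on test and which is the reference; with three arms this cannot be inferred with certainty. And if the normality check selects Mann-Whitney, the p-value cannot be set against a margin of 5 MFI points, and no shift estimate with an interval is named in its place.

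At stake is the primary conclusion. The 80% power belongs to a test that the section does not describe.

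**Working it through.** **Inputs.** From the Statistical analysis section: margin 5, SD 10, alpha 0.01, power 80%, dropout 20%, 100 per group. Assumed because not stated: true difference 0, one pair of arms, and an observed SD equal to the planned 10.

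**1. Reproduce the plan's figure.** Evaluable n per group = 2 × (z for alpha + z for power)² × SD² / margin².
- One-sided 0.01: 2 × (2.326 + 0.842)² × 100 / 25 = 80.3. Dividing by 0.8 gives 100.4 enrolled, which matches 100.
- Two-sided 0.01: 2 × (2.576 + 0.842)² × 100 / 25 = 93.4. Dividing by 0.8 gives 116.8, which does not match.

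The stated number therefore fits one pair at one-sided 0.01 with a true difference of 0.

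**2. Cut-off for the powered test.** With 100 × 0.8 = 80 evaluable per arm, SE = 10 × √(2/80) = 1.581 on 158 degrees of freedom. The half-width of the two-sided 98% interval is 2.350 × 1.581 = 3.72. Non-inferiority needs (observed difference, test minus reference) + 3.72 < 5, so the observed difference must be below 5 − 3.72 = 1.28 points. Power at true difference 0 is 79.1% (noncentral t) or 79.8% (normal approximation), in line with the planned 80%.

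**3. Cut-off for a difference test.** At two-sided 0.01 the result is non-significant up to 2.607 × 1.581 = 4.12 points.

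**4. Set the two side by side.**

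| Observed difference, test minus reference | Difference test, two-sided 0.01 | Margin of 5, one-sided 0.01 |
|---|---|---|
| From −4.12 to below 1.28 | not significant | non-inferiority shown |
| 1.28 to 4.12 | not significant | non-inferiority not shown |
| Above 4.12 | significant, test arm worse | non-inferiority not shown |

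The difference test gives the same answer in the first two rows, although only the first supports the powered conclusion. By simulation, the middle row occurs in about 20% of trials at true difference 0, 40% at 1 point and 58% at 2 points.

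**5. More than one pair.** The documents state no multiplicity rule. If Bonferroni is assumed, two pairs each use one-sided 0.005 and three pairs each use 0.0033. Power per pair at 80 evaluable is then 71.0% or 66.0% (noncentral t).

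**The case against.** **The named t test can do the job.** Run against a null of 5, or reported with its 98% interval, it delivers the planned power from the same patients. This stands: the method is not incompatible with the design. But the section states no such null, and its one sentence also covers hemoglobin, ferritin and the depression score, none of which has a margin. The Mann-Whitney branch has the further problem of scale, though whether it would be reached is unknown.

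**Sidedness is clear enough.** Largely accepted. Higher scores are worse, non-inferiority runs in one direction, and 100 per group reproduces at one-sided 0.01. A reader might infer that the trial is under-sized because two-sided 0.01 would need 117 per group. The documents do not support that: a two-sided reading reaches 80 evaluable only if a true advantage of 0.40 points is assumed ((2.576 + 0.842) × 1.581 − 5 = 0.40), and nothing in the text suggests one. What is missing is the word one-sided.

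**A separate plan exists.** The section says so, and that plan may hold the rule. The point is therefore confined to the supplied text. A reader might infer that the decision rule will be picked after the data are seen; the documents do not establish this.

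**Inconclusive results are normal in non-inferiority trials.** True. At true difference 0, the 20% in the middle row is nearly all of the planned type II error, and a correct rule would not remove it. The percentages show how often a non-significant p-value would fail to support the powered conclusion. They are not an error rate of the plan.

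**Conclusion.** The point holds for the supplied text and must be fixed, because it concerns the primary conclusion. The sample-size sentence plans a non-inferiority test with a 5-point margin. The analysis text describes difference tests without a margin, a pair or a reference arm. Followed as written, those tests do not deliver the conclusion that was powered. The size of the gap is the band from 1.28 to 4.12 points, given 80 evaluable per arm, an observed SD of 10 and alpha 0.01 (one-sided for the margin, two-sided for the difference test). The sample size itself is not in error.

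A reader might also infer that the sponsor will treat a non-significant difference as proof of non-inferiority. Under that reading a true 5-point deficit would pass 29.0% of the time against an intended 1%. The documents nowhere say this will be done, so that figure does not support the finding.

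**What to change.** Add a primary-analysis rule to the Statistical analysis section:

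1. Name the pair tested for non-inferiority, and which arm is the test and which the reference. The gap noted at the end of the Rationale suggests the two intravenous products; the sponsor must confirm this and the direction.
2. Make the primary analysis the two-sided 98% confidence interval for the mean difference in 6-week MFI score, test minus reference. Conclude non-inferiority only if the upper limit is below +5. Do not let the Shapiro-Wilk result switch this analysis to a Mann-Whitney p-value.
3. Add one-sided to the alpha of 0.01, as a clarification.

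If the separate plan already contains such a rule, reproduce it here. If superiority was intended instead, rewrite the sample-size sentence; 80 evaluable per arm give 71% power for a 5-point difference at two-sided 0.01.

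**Cost.** Wording only, with no extra patients, for one pair in one analysis set. If more than one pair shares the 0.01, restate the power per pair: about 71% for two and 66% for three, with Bonferroni assumed. Keeping 80% per pair would instead take 117 or 127 per group (116.8 and 126.4 by the formula in step 1, rounded up).

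### A normality pre-test, not the plan, decides whether the primary fatigue comparison uses means or ranks, and the rank test named cannot be read against the 5-point margin

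*Combined protocol and SAP*

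**What the plan says.** All of this is in the combined protocol and SAP.

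- **Primary outcome** (Outcomes): "Multidimensional Fatigue Inventory (MFI) score at 6 weeks postpartum". No summary measure, mean or median, is attached to it.
- **Secondary outcomes** (Outcomes): hemoglobin, reticulocyte count, ferritin and transferrin are each listed as means, for example "Mean ferritin level at 6 weeks postpartum".
- **Arms** (Methods): women are "allocated randomly in a 1:1:1 fashion into one of three groups", which gives three possible pairs.
- **Sample size** (Statistical analysis): 100 per group for 80% power to show non-inferiority, with "a margin of 5 (half the estimated clinically relevant difference in MFI", an α of 0.01, an SD of 10 and 20% dropout. Whether α is one- or two-sided is not stated.
- **Choice of test** (Statistical analysis): "Shapiro-Wilk test will be used to assess normality of distribution", followed by "Parametric statistics will be carried out for normally distributed variables; for non-normal distribution, we will use nonparametric statistics". The tests are then named: "independent Student's t test or Mann-Whitney U test for continuous and with Chi-square test for categorical variables". Non-normal data are to be described by median and IQR.

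The section gives no level for the Shapiro-Wilk test. It does not say whether the test is applied to all scores pooled, to each arm, to each pair or to residuals, or what happens if arms disagree. It mentions a statistical plan established beforehand, but no further text of such a plan is in the documents.

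**The concern.** The sample size commits the trial to a question about a difference in means: is one treatment worse than another by less than 5 MFI points? The analysis section does not commit to answering it. If the 6-week scores pass the normality test, the result is a comparison of means, from which a difference in points and its confidence interval follow. If they fail, the result is a Mann-Whitney test, which in its standard form tests whether one distribution tends to lie above the other. Its p-value says nothing about 5 points. A shifted version, or a Hodges-Lehmann interval for a location shift, could be set against the margin, but neither is named.

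The same rule conflicts with the outcome list. Four laboratory outcomes are defined as means, yet the rule would report medians and rank tests for any of them that fails Shapiro-Wilk.

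With three arms there is a further gap. Because the unit of the pre-test is not stated, the plan does not exclude judging one pair by means and another by ranks on the same outcome.

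**Working it through.** **1. Reproduce the sample size, to see which scale it is on.** Inputs from the Statistical analysis section: margin 5, SD 10, power 80%, α 0.01, dropout 20%. Assumptions: true difference 0, α one-sided.

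n per arm = 2 × SD² × (z₀.₉₉ + z₀.₈₀)² / margin² = 2 × 100 × (2.326 + 0.842)² / 25 = 80.3, so 81.

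Dropout: 81 / 0.8 = 101.3, so 102; or 81 × 1.2 = 97.2, so 98. Both are close to the stated 100. With two-sided α 0.01 the result is 94 evaluable, or 113 to 118 after dropout, which does not match. The stated figure is therefore a comparison of means at one-sided 0.01.

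At 80 evaluable per arm (100 × 0.8), the standard error is 10 × √(2/80) = 1.581. Then 5 / 1.581 − 2.326 = 0.836, and power is Φ(0.836) = 79.8%.

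**2. How often would the pre-test select ranks, and would the pairs agree?** The documents do not give what this needs, so these are assumptions: Shapiro-Wilk at 0.05; 80 women per arm; the same distribution in all arms; mean 50, SD 10; normal or gamma-shaped skew; scores rounded and held to 20–100. There were 4,000 simulated trials per row, so the simulation standard error is at most √(0.25/4000) = 0.8 percentage points.

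| Skewness | Ranks chosen, one pooled test (n = 240) | Pairs get different tests, tested by arm* | Pairs get different tests, tested by pooled pair |
|---|---|---|---|
| 0 (normal) | 6% | 13% | 13% |
| 0.25 | 33% | 29% | 38% |
| 0.40 | 65% | 41% | 51% |
| 0.50 | 84% | 44% | 48% |
| 0.67 | 98% | 33% | 24% |

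*Ranks used if either arm of the pair fails.

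With one pooled test, all three pairs share a method by construction, so mixing is 0%.

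**3. Does the rule damage error rates?** One non-inferiority comparison was simulated at one-sided 0.01 with 80 per arm, 5,000 trials per setting, skewness 0, 0.5, 0.67 and 1.0, and equal shapes. The Mann-Whitney test was given the benefit of a shift by the margin, which the plan does not provide.

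- Type I error (true difference 5): two-stage rule 0.009 to 0.012; t test throughout 0.009 to 0.013. The simulation standard error is √(0.01 × 0.99 / 5000) = 0.0014, so these are indistinguishable from 0.01.
- Power (true difference 0): two-stage rule 0.79 to 0.85; t test throughout 0.78 to 0.80.

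The t test therefore holds its level at this size up to skewness 1.0, and normality is not needed to protect it.

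**4. What does the Mann-Whitney test show without the shift?** In the same simulations, tested two-sided at 0.05, it is significant in 87% to 92% of trials when the true difference equals the margin, and in about 5% when there is no difference. It is a test of difference. Neither a significant nor a non-significant result establishes that the difference is below 5 points.

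**The case against.** The strongest reply has four parts.

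- **The rule is written in advance and worded per variable.** MFI at 6 weeks is one variable, so the natural reading is one pre-test and one method for all pairs. This stands. A reader might infer that the plan makes the three pairs be judged by different tests; the text does not say so. It leaves the unit of testing open, and mixing arises only if testing is by arm or by pair.
- **The mixing percentages rest on settings the plan does not contain.** This also stands. In a second model (scaled beta, tested by arm), mixing was 14%, 30%, 45% and 20% at skewness 0, 0.25, 0.4 and 0.6 with a 0.05 pre-test. With a 0.01 pre-test it was 2%, 9%, 27% and 43%. These figures show that the gap can matter; they do not predict this trial.
- **No error rate is shown to suffer.** This stands too. A reader might infer that the pre-test inflates type I error, but the simulations do not support that. Where the shifted Mann-Whitney and t tests were compared with no true difference, they disagreed on non-inferiority in about 5–6% of comparisons.
- **A change to medians is conditional.** It happens only where normality is rejected. This is correct, and the point is put in that form.

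None of this answers the central difficulty. If ranks are selected, the plan names no analysis that can be set against its own margin, whether the pre-test is pooled, by arm or by pair.

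**Conclusion.** The point holds as one about an unfixed primary effect measure. A Shapiro-Wilk result on the trial's own data chooses between a t test and a Mann-Whitney test for the primary outcome, and only the first leads to a quantity on the scale of the 5-point margin. Under one pooled pre-test at an assumed 0.05 level, the chance of landing on ranks runs from about 6% with normal scores to 98% at skewness 0.67. Skewness that leaves the t test unharmed at 80 per arm can therefore decide the primary method. The outcomes named as means are exposed to the same switch.

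Whether methods could differ between pairs is an ambiguity, not a stated feature: 0% with a pooled test, and roughly 13–51% of trials with testing by arm or pair at 0.05 under the shapes in the table. The documents do not support a claim of inflated type I error, lost power or a wrong sample size. The simulations assume equal shapes across arms, and the skewness of 6-week MFI scores is not given in the documents.

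**What to change.** In the Statistical analysis section:

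1. Drop the normality gate for MFI and for hemoglobin, reticulocyte count, ferritin and transferrin.
2. Name one mean-difference analysis for all pairs, for example a linear model with the three groups as a factor, to be used whatever Shapiro-Wilk shows.
3. For MFI, report each pairwise mean difference with its confidence interval and read it against the 5-point margin. If α is confirmed as one-sided 0.01, as the sample size implies, the matching two-sided interval is 98% (1 − 2 × 0.01). State this explicitly, because a t test against zero does not address the margin either.
4. Keep Mann-Whitney as a sensitivity analysis only. Medians and IQRs can still be shown descriptively beside the means.

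The cost is wording, to be settled before outcome data are examined. The stated sample size is unchanged: 81 evaluable per arm, with 79.8% power at 80.

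### Six-week hemoglobin is to be compared without adjustment for baseline hemoglobin, although every woman has a baseline value: a possible, perhaps very small, gain in precision on a secondary outcome is not used.

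*Combined protocol and SAP*

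**What the plan says.** The Statistical analysis section of the combined protocol and SAP gives one rule for all continuous outcomes: "Comparisons will be carried out between the study groups using independent Student's t test or Mann-Whitney U test for continuous" variables, with a Shapiro-Wilk test deciding between the two. It names no covariate, regression or change score, and it plans no confidence interval. The section opens with "All data will be analyzed according to a pre-established statistical plan", but no further plan is in the text available.

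Three other places bear on the point:

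- Secondary outcomes lists "Mean hemoglobin level at 6 weeks postpartum".
- Inclusion criteria admits "Postpartum patients with a hemoglobin level between 70 g/L and 100 g/L within 48 hours after delivery". The same variable is therefore known at baseline for every woman in all three arms.
- Methods sets the total IV iron dose in both IV arms by "prepregnancy weight in kilograms X (15–baseline Hb) X 2.4 + 500". In the third arm, "Participants will receive oral ferrous sulphate (Tardyfer®) 160 mg daily for 6 weeks". The IV dose thus depends on baseline hemoglobin and the oral dose does not.

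**The concern.** When a baseline value of the outcome is already in hand and predicts the later value, a model that includes it estimates the same mean difference between arms with a smaller standard error. An unadjusted comparison forgoes that.

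At stake is the precision of the hemoglobin contrasts. The trial's objective is efficacy in postpartum anemia, which hemoglobin measures directly. One contrast has no earlier data according to the Rationale: "No study to date, however, compared efficacy of iron carboxymaltose to iron isomaltoside for treatment of postpartum anemia".

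It also matters when the choice is made. An adjustment picked after the data are seen is open to the charge of selection. The form of the model is not obvious either, because the relation of baseline to 6-week hemoglobin may differ between arms with a tailored dose and an arm with a fixed dose.

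**Working it through.** **The plan's own figure.** The only sample size stated is for the Multidimensional Fatigue Inventory (MFI): margin 5, SD 10, α 0.01, 80% power, 20% dropout, 100 per group. With α taken as one-sided:

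n = 2 × [10 × (2.326 + 0.842)/5]² = 80.3 completers per arm; 80.3/0.8 = 100.4.

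The stated 100 reproduces. It does not concern hemoglobin and is not affected by this point. It supplies the number used below: 100 less 20% = 80 completers per arm.

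**Inputs not in the documents (assumed).** The correlation r of baseline with 6-week hemoglobin, equal in the two arms compared; an SD of 10 g/L for 6-week hemoglobin; a 95% interval.

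**Variance relative to the t test.** For one pair of arms, the ratio of adjusted to unadjusted variance is

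(1 − r²) × [1 + 1/(2×80 − 4)] = (1 − r²) × (1 + 1/156).

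The second factor is the cost of estimating the slope, 0.64%. The 95% half-width is t(0.975) × 10 × √(ratio × 2/80). Degrees of freedom are 158 unadjusted and 157 adjusted, and t is 1.975 in both. Unadjusted: 1.975 × 10 × √0.025 = 3.12 g/L.

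| Assumed r | Variance ratio | Change in variance | Change in width | Half-width, g/L |
|---|---|---|---|---|
| 0 | 1.0064 | +0.6% | +0.3% | 3.13 |
| 0.1 | 0.9963 | -0.4% | -0.2% | 3.12 |
| 0.2 | 0.9662 | -3.4% | -1.7% | 3.07 |
| 0.3 | 0.9158 | -8.4% | -4.3% | 2.99 |
| 0.5 | 0.7548 | -24.5% | -13.1% | 2.71 |

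The half-widths scale with the SD. For SD 8 and 12 g/L they are 2.50 and 3.75 unadjusted, 2.39 and 3.59 at r = 0.3, and 2.17 and 3.26 at r = 0.5. At a 99% level and SD 10 the unadjusted half-width would be 4.12 g/L; the relative changes barely move.

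**Where r is likely to lie.** Two features of the design point to low values.

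- Entry confines baseline to a 30 g/L range. If values were uniform over it, their SD would be 30/√12 = 8.7 g/L.
- In the IV arms the dose offsets a low baseline. At an assumed 60 kg the plan's formula gives 60 × (15 − 7) × 2.4 + 500 = 1652 mg at 70 g/L and 60 × (15 − 10) × 2.4 + 500 = 1220 mg at 100 g/L, a difference of 432 mg (360 to 576 mg for 50 to 80 kg). This tends to flatten the slope in both IV arms. It does not act in the oral arm.

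**Why the form of the model matters.** Take r = 0 in both IV arms and 0.5 in the oral arm, with baseline uniform on 70-100 g/L and 80 per arm. In a simulation of 40,000 runs, the changes in variance against the unadjusted difference were:

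| Comparison | One common slope over three arms | Separate model for each pair |
|---|---|---|
| IV versus IV | +3.4% | +0.6% |
| IV versus oral | -5.0% | -5.5% |

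An arm-by-centred-baseline term fitted per pair came within 0.2 percentage points of the pairwise result. Across the unequal-slope settings tried, robust (HC3) 95% intervals from the pairwise models covered the true difference in 95.0 to 95.4% of runs.

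**The case against.** The strongest case against is that this is a preference. The planned tests are valid, the outcome is secondary, and the documents state no SD, power, margin or decision rule for hemoglobin, so no stated conclusion is shown to depend on the change. The gain may be nil, and for IV versus IV a loss below 1% is plausible. No confidence interval is planned, so none can be called too wide. If hemoglobin is judged non-normal the plan turns to Mann-Whitney, and the figures above do not address that comparison. Further details may sit in the statistical plan to which the section refers.

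Much of this stands. It limits the point to a possible gain and gives it low priority. It does not remove it: the plan states a method, and a specific alternative costs about 0.6% of variance at worst in the recommended form and may save much more. If the adjustment is already planned elsewhere, one sentence settles the matter.

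A reader might infer three stronger things that the documents do not support:

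- That the unadjusted tests are biased or inflate the type I error. Randomization makes them valid.
- That a 25% reduction in variance is available. That needs r = 0.5, for which the documents give no basis and which the design makes doubtful in the IV arms.
- That the point extends to MFI or the other outcomes. No baseline MFI is mentioned, and nothing given relates baseline hemoglobin to 6-week MFI. Nor is a figure offered for the outcome "Proportion of participants with hemoglobin level > 120 g/L at 6 weeks postpartum", because the documents do not give the distribution of 6-week hemoglobin around that cut.

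**Conclusion.** The point holds as a low-priority improvement to one secondary outcome. For 6-week hemoglobin the stated analysis leaves aside a baseline value that every woman has. The consequence lies between a negligible loss and a useful gain, and the documents cannot say where in that range; the reasons given above favor the low end, most of all for IV versus IV. Any gain is more plausible in comparisons that involve the oral arm. The range rests on 80 completers per arm and the assumed r; the figures in g/L rest also on the assumed SD and on a 95% level that the plan does not state (its only α, 0.01, belongs to MFI).

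**What to change.** Add to the Statistical analysis section, for 6-week hemoglobin only and before any outcome data are seen:

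- a linear model with arm and baseline hemoglobin, fitted separately for each pairwise comparison of arms, or with an arm-by-centred-baseline term to allow for different slopes in IV and oral arms;
- the adjusted mean difference with a heteroscedasticity-consistent confidence interval, its level stated;
- the unadjusted test kept as supportive.

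Do not extend the adjustment by default to other outcomes or to the proportion above 120 g/L.

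The cost is a few lines of text and no new data, visits or participants. Each model uses one extra degree of freedom (one more with the interaction term), and the variance rises by about 0.6% if baseline hemoglobin predicts nothing. The robust interval may need one extra calculation step. The sample size does not change.

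### Comparing IV iron costs without adjusting for the baseline calculated dose is valid but less precise than it need be

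*Combined protocol and SAP*

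**What the plan says.** The secondary outcomes list includes "Costs of treatments" without saying which components are counted or at what prices. For continuous outcomes the Statistical analysis section gives one rule: "Comparisons will be carried out between the study groups using independent" t or Mann-Whitney tests, chosen by a Shapiro-Wilk check. It names no covariate. It mentions a pre-established statistical plan, but the document contains no further plan.

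Under METHODS, the carboxymaltose arm uses a modified Ganzoni formula. The isomaltoside total dose "needed to correct anemia and replenish iron stores will be calculated as described above", so both arms share the formula. They differ in the most that may be given in one day: 15 mg/kg or 1000 mg for carboxymaltose, and 20 mg/kg or 1500 mg for isomaltoside. In both arms the remainder follows at weekly visits. The end of the RATIONALE says that the only earlier head-to-head comparison of the two products was economic, "showing potential reduction of costs associated with the use of iron isomaltoside vs. iron carboxymaltose".

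**The concern.** Under randomisation the two intravenous arms have the same expected calculated dose. Differences in dose between women therefore carry no information about which product costs more, yet they make up much of the spread in cost. What the plan makes systematically different is the number of infusions, plus any difference in unit price. Calculated dose is fixed at baseline and must be worked out to treat every woman in these arms, so it is a free covariate that the planned test leaves in the error term. At stake is whether the trial can say anything firm on the one question on which, by its own account, these products have already been compared.

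**Working it through.** **The plan's own figure.** No power is stated for cost. The stated size, "The planned sample size of 100 patients per group", concerns the fatigue score: "80% power to detect non-inferiority using a margin of 5", "an α of 0.01", "expected standard deviation (SD) of 10". With one-sided 0.01, n = 2 × (10/5)² × (2.326 + 0.842)² = 80.3, and 80.3/0.8 = 100.4, so it reproduces. For the cost question it only fixes the numbers: 100 per arm, or 80 after the assumed dropout.

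**Inputs from the protocol.** Dose D = 2.4 × W × (15 − Hb) + 500 mg, with W the prepregnancy weight and Hb in g/dL from 7 to 10. Infusions = D divided by the single-day cap, rounded up.

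**What the caps do.** At Hb 10 the formula is 12W + 500, which exceeds 1000 mg once W is above 500/12 = 41.7 kg. Practically every carboxymaltose woman therefore needs at least two infusions. For isomaltoside it depends on the woman. Take W = 65 kg and a current weight of 72 kg (cap 20 × 72 = 1440 mg). At Hb 9, D = 2.4 × 65 × 6 + 500 = 1436 mg, which is one infusion. At Hb 8, D = 1592 mg, which is two.

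**Assumptions (not in the documents).** Prepregnancy weight has mean 60-72 kg and SD 10-15; current weight is 7 kg higher; Hb is spread over 7-10 g/dL, uniformly or skewed upward. Price per mg is equal, adherence is full, there are 100 per arm, and testing is two-sided at 0.05. A visit is priced in mg of iron.

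**Noise from dose.** D averages 1370-1624 mg with SD 169-275 mg. The 95% chance range for the difference in mean dose is ±1.96 × √(2/100) × SD. That is ±47 mg (47/1370 = 3.4%) to ±76 mg (76/1624 = 4.7%).

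**Signal from infusions.** Mean infusions are 2.0-2.1 for carboxymaltose and 1.65-1.84 for isomaltoside. At 200 mg per visit the true cost difference is worth 47-70 mg of iron, about the same size as that chance range.

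**Power** = Φ(difference/SE − 1.96). The unadjusted SE is √((var₁ + var₂)/100) = 27-45. The adjusted SE, from residuals after regressing cost on D, is 8-10.
- Heavier population: difference (2.10 − 1.84) × 200 = 52. Unadjusted: Φ(52/45 − 1.96) = Φ(−0.80) = 21%. Adjusted: 52/8 = 6.5 standard errors, above 99%.
- Lighter population, Hb skewed upward: difference (2.00 − 1.65) × 200 = 70. Unadjusted: Φ(70/27 − 1.96) = Φ(0.63) = 74%, or up to 78% depending on how the Hb skew is drawn. Adjusted: 70/10 = 7 standard errors, above 99%.

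| Visit cost (mg of iron) | Later infusions missed | Unadjusted | Adjusted for D |
|---|---|---|---|
| 100 | none | 9-29% | 98% or more |
| 200 | none | 21-78% | above 99% |
| 400 | none | 52-99% | above 99% |
| 200 | 10% | 5-16% | 5-29% |
| 400 | 10% | 12-68% | 20-87% |

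**Second calculation, wider populations, 80 per arm, full adherence.** At 200 mg per visit, unadjusted power is 16-91%; at 1000 mg it is 83% to above 99%. Adjusted power is 97% or more throughout.

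**Choice of test.** Once a visit costs about 500 mg of iron or more, the normality rule mostly selects Mann-Whitney. Its power then levels off at 16-48% in three of four simulated populations (99% in the fourth, with a narrow spread), because it ranks largely on dose.

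**The case against.** The strongest objection is adherence. The near-certain adjusted power arises because, with full adherence, cost is an exact function of baseline data. The plan allows for 20% dropout, and later doses need weekly return visits. Missed infusions add variation that baseline dose cannot explain. They also shrink the true difference, because carboxymaltose leaves more drug for the second visit: at 200 mg per visit, 10% missed cuts it from 47-70 to about 2-27 mg of iron. At 20% missed, neither analysis exceeds 22% power at 200 or 400 mg per visit. This objection stands, and it removes much of the gain. Adjustment did not lower power in any scenario run.

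Prices are the second objection. At full adherence and 100 per arm, the unadjusted t test has 93% power or more if a visit costs as much as 1 g of iron or isomaltoside is 10% cheaper per mg. If isomaltoside is 10% dearer, price and infusion effects can cancel, and no adjustment changes that. This also stands.

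Third, the infusion count itself is not hidden. The difference is at least 47/200 = 0.235 with an SE of at most 0.048, about 5 standard errors, without any covariate.

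Three stronger readings are tempting, and the documents do not support them:
- A reader might infer that dose variation swamps the cost difference. That depends on prices and adherence that the protocol does not give.
- A reader might infer that the dosing rules themselves create a cost difference. They create a difference in infusions, not in drug quantity. If only drug is counted at equal price per mg, the rules create no difference.
- A reader might fear that a significant result would merely reflect chance imbalance in weight and hemoglobin. Under randomisation the unadjusted test already holds that risk at its nominal level.

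**Conclusion.** The point holds as one of precision, not validity. The planned comparison is unbiased, but it leaves in the error term a quantity that is known at baseline and identically defined in both intravenous arms. The gain from adjusting is large when per-mg prices are similar, a visit costs well under 1 g of iron and most infusions are given. It is modest when infusions are missed. At full adherence it is small when a visit costs about 1 g of iron (with the t test) or isomaltoside is some 10% cheaper per mg. All weight, hemoglobin, price and adherence inputs are assumptions, and vial wastage was not modelled. Cost is one of several secondary outcomes with no stated power, and the trial's objective is efficacy, so this is a worthwhile refinement rather than a defect that threatens the trial.

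**What to change.** In the Statistical analysis section, define cost per woman as drug plus administration. State that carboxymaltose and isomaltoside will be compared with a linear model of cost on arm and the total dose calculated at baseline. Report the adjusted mean difference with its 95% CI, beside the observed cost and number of infusions in each arm.

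A table applying both arms' dosing rules to each woman's baseline data may be added as optional support, labelled as planned rather than actual cost. If it covers the oral arm, weight must be recorded there too.

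The change takes a sentence or two and a short analysis that SPSS, already named in the plan, can run. It needs no new patients, visits or tests and leaves treatment unchanged.
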